8.4. Data sources

The primary data source will be data collected through a DCT. Bonical Emas is the vendor responsible for facilitating capture of HCP responses in DCT via EDC. Bonical Emas is also responsible for de-identification of patient level information. Anonymized pathology reports

PFIZER CONFIDENTIAL

submitted as part of the initial lorlatinib request will be summarized and entered into the DCT by Pfizer to confirm information such as ALK aberration testing and status.

As part of Pfizer's expanded access program, HCPs report a full description of Adverse Events (AEs) to the local Pfizer Drug Safety Unit (DSU) using the expanded access adverse event report. AEs captured by the local Pfizer Drug Safety Unit (DSU) will be compared and reconciled to the AEs captured in the DCT and used to summarize the reported AEs. Upon resupply request the requesting HCP certifies that safety reporting has been done per Pfizer expanded access program requirements. Safety information will also be collected in the DCT as the HCP reviews the patient chart as outlined in [Section 10](#).

8.5. Study size

With primary goal of the Pfizer expanded access program is to provide treatment access to patients with an unmet clinical need, no formal power calculations were conducted to determine sample size. Furthermore, the data collection does not involve hypotheses testing (via statistical testing) and it is primarily being conducted to understand treatment outcomes. Target sample size will comprise every patient fulfilling eligibility criteria above and providing informed consent for real world data collection.

8.6. Data management

Bonical Emas will implement Data Management practices for collating and managing the data. These include (1) HCP access management and training, (2) data review, and (3) database storage and retention.

HCP Access Management and Training:

Bonical Emas will add HCPs to the EDC using details obtained from Pfizer after confirmation of patient eligibility and HCP agreement. HCP information will include: HCP name, country, location.

Data Review:

Data review is iterative process to ensure integrity and quality of data. Bonical Emas will ensure data are complete, reliable and processed correctly.

8.6.1. Case report forms (CRFs)/Data collection tools (DCTs)/Electronic data record

As used in this protocol, the term DCT should be understood to refer to either a paper form or an electronic data record or both, depending on the data collection method used in this study.

A DCT is required and should be completed for each included patient. The completed original DCT are the sole property of Pfizer and should not be made available in any form to third parties, except for authorized representatives of Pfizer or appropriate regulatory authorities, without written permission from Pfizer. The HCP shall ensure that the DCTs

PFIZER CONFIDENTIAL

securely stored in encrypted electronic form and will be password protected to prevent access by unauthorized third parties.

The HCP has ultimate responsibility for the collection and reporting of all clinical, safety, and laboratory data entered on the DCT and any other data collection forms (source documents) and ensuring that they are accurate, authentic/original, attributable, complete, consistent, legible, timely (contemporaneous), enduring, and available when required. The DCT must be electronically signed by the HCP or by an authorized staff member to attest that the data contained on the DCT are true. Any corrections to entries made in the DCT or source documents must be dated, initialed, and explained (if necessary) and should not obscure the original entry.

In most cases the source documents are the hospital or the HCP's chart. In these cases, data collected on the DCT must match those charts.

In some cases, the DCT may also serve as the source document. In these cases, a document should be available at the HCP site and at Pfizer that clearly identifies those data that will be recorded on the DCT, and for which the DCT will stand as the source document.

8.6.2. Record retention

[figure not shown]
To enable evaluations and/or inspections/audits from regulatory authorities or Pfizer, the HCP agrees to keep records, including the identity of all participating patients (sufficient information to link records, e.g., DCT and hospital records), all original signed informed consent/assent documents, copies of all DCT, safety reporting forms, source documents, detailed records of treatment disposition, and adequate documentation of relevant correspondence (e.g., letters, meeting minutes, and telephone call reports). The records should be retained by the HCP according to local regulations or as specified in the clinical study agreement (CSA), whichever is longer. The HCP must ensure that the records continue to be stored securely for so long as they are retained.

If the HCP becomes unable for any reason to continue to retain study records for the required period (e.g., retirement, relocation), Pfizer should be prospectively notified. The study records must be transferred to a designee acceptable to Pfizer, such as another HCP, another institution, or to an independent third party arranged by Pfizer.

HCP records must be kept for a minimum of 15 years after completion or discontinuation of the study or for longer if required by applicable local regulations.

The HCP must obtain Pfizer's written permission before disposing of any records, even if retention requirements have been met.

PFIZER CONFIDENTIAL

8.7. Data analysis

Bionical Emas in collaboration with Syne Qua Non Limited (SQN) will perform the data analyses described in this protocol using SAS statistical software. Statistical summaries, figures and listings will be produced using SAS (version 9.4 or later).

All development of data summaries and analyses will be documented and retained for traceability including dataset specifications and derivations, name of the programmed outputs and assigned program authors and reviewers.

All data outputs will be fully quality controlled including review of the logs and associated outputs.

No formal statistical testing is planned, and all data analyses will be descriptive and explorative.

8.7.1 Data Reporting Milestones

Data on patients who have completed treatment, patients receiving ongoing treatment and new patients will be captured. The plan is to report the data collectively and cumulatively with the first data reporting to provide an initial assessment of a group of patients having completed treatment. Patients who completed treatment by the time data collection is initiated (completed treatment prior to January 2021) will be those included in the initial progress report. Data reporting will be provided annually thereafter with a final report as outlined in [Section 5](#).

8.7.2 Analysis Set

Data summaries and listings will be produced on all the data collected, regardless of patients fulfilling the inclusion and exclusion criteria detailed in [Section 8.2.1](#) and [Section 8.2.2](#).

8.7.3 Patient Disposition and Demography

Patient disposition will account for the number of patients receiving treatment, continued treatment and discontinued treatment at a specific milestone. Potential reasons for discontinuing treatment will include disease progression, adverse event excluding death, death, lost to follow up, and other.

Demographic and patient characteristics will include variables as noted in [Section 8.3](#). Additional variables will be statistically derived and reported including time since initial diagnosis. Time since initial diagnosis, in months, will be derived as: $12*((\text{Date of initial diagnosis}) - (\text{First Date of lorlatinib Treatment}) + 1) / 365.25$.

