Partial Response (PR)	PR in at least one component and all other components are either CR, MD (Bone marrow), PR (Soft tissue or Bone) or Not involved (NI); no component with PD.													
Minor Response (MR)	PR or CR in at least one component but at least one other component with SD; no component with PD.													
Stable Disease (SD)	SD in one component with no better than SD or NI in any other component; no component with PD.													
Progressive Disease (PD)	Any component with PD													
Best Overall response	HCP Reported Response	Derived as the best overall response taking the HCP Reported Response observed up to the data cut-off date for a specific milestone. (The												

PFIZER CONFIDENTIAL

	Repeated using Derived Objective Response	sequence order from best to worst is CR, PR, MR, SD, PD.)
Overall Response Rate (ORR)	Best Overall Response	Derived as Best overall response of CR+PR of the total population observed up to the data cut-off date for a specific milestone.
Duration of response	Treatment Start and HCP Reported Response Date	Derived as (Date of PD or death, whichever occurs first) – (Date of PR or CR, whichever occurs first) + 1
Progression free survival (PFS)	Treatment Start and HCP Reported PD/Death Date	Derived as (Date of PD or death (by any cause in the absence of PD)) – (Treatment start date) + 1
Duration of treatment	Treatment Start and Stop Dates	Derived as (Treatment stop date) – (Treatment start date) + 1
Overall survival (OS)	Treatment Start and Death Dates	Derived as (Date of death) – (Treatment start date) + 1

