8.7.6 Statistical summaries

Demographic and clinical characteristics

The number and percentage of patients will be presented within each categorized variable. In addition, descriptive statistics for continuous variables will include the mean, standard deviation, median, interquartile range, minimum and maximum.

The demographics will also be presented by subgroups for any subgroups with more than 5 patients.

HCP's reported objective response

For each response component (with the exception of best response), the responses will be listed along with the date of the assessment. A derived objective response will be produced and compared to the HCP overall reported response for confirmation of robustness.

Best Overall Response (BOR) and Overall Response Rate (ORR)

For the BOR, the number and percentage of patients in each ordered category will be presented and summarized by baseline disease status. In addition, the ORR will be presented including the Clopper Pearson 95% Confidence interval.

PFIZER CONFIDENTIAL

Duration of response

The number and percentage of patients will be presented within each of the following categories for duration of response: 0 to <3 months; 3 months to <6 months; 6 months to <1 year; 1 to <2 years; 2 to <3 years >3 years; lost to follow-up. Kaplan-Meier (KM) estimates will be used to give the median, Q1 and Q3 duration of response, with 95% confidence limits. If a patient does not show symptoms of progressive disease, their duration of response will be censored at their last visit date prior to the data cut-off date.

Time to event

KM estimates will be presented, where possible, for duration of treatment, progression free survival and overall survival (i.e., time to death). The following censoring rules will be applied:

- Duration of treatment

Patients who have not discontinued treatment at the data cut-off date will be censored based on the last recorded date when the patient was known to be continuing treatment prior to the data cut-off date.

- Progression free survival

Patients who have not experienced PD or died at the data cut-off date will be censored at the date of last contact prior to the data cut-off date.

- Overall survival

[figure not shown]
Any patient not known to have died at the data cut-off date will be censored based on the last recorded date on which the patient was known to be alive prior to the data cut-off date.

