The KM curves will be used to estimate the median, Q1 and Q3 survival times, with 95% confidence limits. The proportion of patients with an event will also be estimated from the corresponding Kaplan-Meier curves with 95% confidence limits.

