8.7.8 Missing data

Statistical summaries, figures and listings will be based on all available data, as observed. Missing data will not be imputed with the exception of partial dates as per below. However, the amount of missing data will be reported.

For the endpoints requiring date derivations such as duration of response, time to event, the following imputation for partial dates will be applied:

- Missing year: no imputation with date remaining as missing
- Missing month: impute as month 6 (June, mid-year approximately)
- Missing day: impute as 15 (mid month approximately)

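### Minor: time since initial diagnosis is subtracted the wrong way round and prints negative months; secondarily, the June/15th date imputation has no date-order bound

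*Combined protocol and SAP*

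**What the plan says.** Section 8.7.3 gives the formula for time since initial diagnosis. The part between the outer brackets reads "Date of initial diagnosis}) - (\text{First Date of lorlatinib Treatment}) + 1" (the braces are typesetting residue). It is multiplied by 12 and divided by 365.25 to give months.

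Section 8.7.5 defines four durations: duration of response, progression-free survival (PFS), duration of treatment and overall survival (OS). Each is the later date minus the earlier date, plus 1. The OS entry is "Derived as (Date of death) – (Treatment start date) + 1", and the duration of response formula ends by subtracting "Date of PR or CR, whichever occurs first) + 1".

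Section 8.7.8 sets a rule for partial dates, scoped as "For the endpoints requiring date derivations such as duration of response, time to event". It has two imputing clauses, "Missing month: impute as month 6 (June, mid-year approximately" and "Missing day: impute as 15 (mid month approximately"; a missing year is left missing. It does not relate an imputed date to treatment start, response, progression (PD), death, last contact or data cut-off.

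Section 8.7.6 then uses the durations. Duration of response is tabulated in categories that begin "0 to <3 months; 3 months to <6 months; 6 months to <1 year", and for the time-to-event endpoints "The KM curves will be used to estimate the median, Q1 and Q3 survival times, with 95% confidence limits".

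**The concern.** Two things look wrong.

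- **(a) Direction.** Diagnosis precedes first lorlatinib dose in this setting: Section 7 describes an expanded access program for patients who have used up the standard options. Earlier minus later gives a negative number for essentially every patient. If programmed as written, the baseline table would show negative months since diagnosis.
- **(b) Date order.** With plus 1 in each formula, the smallest possible duration is 1 day. An imputed progression, death or stop date can nevertheless fall before treatment start or first response, and an imputed response date can fall after a known PD. The result is then 0 or less. A value of 0 still fits the lowest duration-of-response category; a negative value fits none and has no place on a Kaplan-Meier time axis. The plan does not say whether such a record is dropped, reset or queried, so the handling becomes an unstated programming choice.

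**Working it through.** **(a) Time since initial diagnosis.** Let g be the days from diagnosis to first dose. The gaps below are illustrations; 396 days is about the 13-month median time to relapse in Section 6 (13 × 365.25/12 = 395.7).

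- As printed: 12 × (-g + 1)/365.25. With dates swapped: 12 × (g + 1)/365.25.
- g = 0: +0.03 both ways. g = 1: 0.00 printed. g = 2: -0.03 printed.
- g = 396: 12 × (-395)/365.25 = -12.98 printed; 12 × 397/365.25 = +13.04 swapped.
- g = 730: 12 × (-729)/365.25 = -23.95 printed; 12 × 731/365.25 = +24.02 swapped.
- Absolute value of the printed form: g - 1 days instead of g + 1, so 2 days short (24/365.25 = 0.066 months) for every gap of 1 day or more.

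**(b) Imputed dates.** Example dates are assumed; formulas are from Section 8.7.5 and imputation from Section 8.7.8.

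- Start 10 Sep 2019, death 2019 (month missing): 15 Jun - 10 Sep + 1 = -86 days of OS. Feasible: 1 to 113.
- Start 20 Mar 2019, stop Mar 2019 (day missing): 15 Mar - 20 Mar + 1 = -4 days of treatment.
- Start 5 Jan 2019, response 2019 (month missing), PD 10 Apr 2019: 10 Apr - 15 Jun + 1 = -65 days of response. Feasible: 1 to 96.

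*Calendar tallies (2019), values of 0 or less.* For a partial end date in the start year with the month missing, 199 of 365 start dates; in the start month with the day missing, 185 of 365. For a partial response date with PD known, 165 of 365 PD dates (month missing) and 168 of 365 (day missing). These weight every date equally and are not event rates.

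*As a rate.* Assume exponential times with a 6-month median (rate ln 2/0.5 = 1.386 per year) and uniform start dates.

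- Event in the start year: 1 - (1 - e^(-1.386))/1.386 = 0.459.
- Start on 16 June or later and event in that year: 0.545 - (1 - e^(-1.386 × 0.545))/1.386 = 0.163.
- Ratio: 0.163/0.459, about 35%, against the tally's 199/365 = 55%.

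*Patients affected.* Assume 50 patients (the maximum in Section 8.1), all with an event, and 2%, 5% or 10% of end dates missing the month. Then 50 × 0.05 × 0.163 = 0.4, with 0.16 and 0.81 at the other two rates. For medians from 4 to 16.1 months (the latter is the OS figure in Section 6), the count exceeds one only at 4 months with 10% missing: 50 × 0.10 × 0.220 = 1.10.

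*Effect on Kaplan-Meier estimates* (simulation under the same assumptions, partial end dates only; shifts in days at 2% / 5% / 10%):

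| Handling | Median | Q1 |
|---|---|---|
| Reset to day 1 | -0.03 / -0.07 / -0.15 | -0.35 / -0.89 / -1.82 |
| Drop the record | +0.9 / +2.1 / +4.2 | +0.8 / +1.8 / +3.2 |

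Over medians of 4 to 16.1 months, the median shift runs from -0.8 (reset) to +5.0 days (dropped).

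*Sampling error of the median.* Large-sample SD = median/(ln 2 × √n) = 182.6/(0.693 × 7.07), about 37 days.

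**The case against.** On (a), the intent is obvious and the first output would expose the sign. Section 8.7 requires full quality control of outputs. That limits the harm, but the printed formula remains wrong, and the quick repair of dropping the sign leaves a 2-day error.

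On (b), the defence is stronger. Section 8.7.8 contradicts nothing, the study is descriptive without hypothesis tests, and Section 8.7 provides for documented dataset specifications where an order rule could sit. Inclusion criterion 2 and visits every 3-4 months make very early events less likely. With an assumed 28 event-free days, the share affected at a 6-month median falls from 16.3% to 14.2% of month-missing events and from 1.6% to 0 of day-missing events, although Section 8.7.2 summarizes all data collected whether or not criteria are met. All this supports treating (b) as a small completeness gap. It does not remove the gap: the checks in Section 8.8 run when data are saved, before imputation, and no section states an order rule.

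A reader might infer more than the documents support:

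- *That over half of partial dates would fail.* The 199 of 365 and similar counts are calendar tallies. Events in the start year come mostly from early-year starts, so the modelled share is about 35% of month-missing events in that year.
- *That the survival or response results are materially distorted.* The expected shifts are small beside sampling error, and the number of partial dates is unknown.
- *That the sign error reaches the effectiveness endpoints.* All four formulas in Section 8.7.5 run in the correct direction.

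**Conclusion.** Minor, but wrong as written.

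Part (a) is certain from the text. It reverses the sign of one descriptive baseline variable for any patient diagnosed two or more days before first dose, and touches no effectiveness endpoint.

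Part (b) is secondary and conditional. It needs a partial date close enough to its paired date, in the same month or year. The plan gives no expected number of partial dates, so the 2-10% rates, the exponential times, the 6-month median and the full 50 patients with events are all assumptions. Under them, probably fewer than one patient per endpoint is affected and the median shifts by at most a few days, against a sampling SD of about 37 days. The Kaplan-Meier effect of misplaced response dates was not computed. The case for acting is that impossible values should have a pre-stated handling, not that the results are at risk.

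**What to change.** **Section 8.7.3.** Replace the formula with 12 × ((First date of lorlatinib treatment) - (Date of initial diagnosis) + 1)/365.25. Do not use the absolute value of the present one.

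**Section 8.7.8.** Keep the June and 15th defaults and add:

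- If an imputed date falls outside the interval set by its known month or year and the patient's other known dates (treatment start, first response, treatment stop, PD, death, last contact and data cut-off, as applicable), set it to the nearest feasible date.
- If two paired dates are both partial, impute the earlier event first and use it as the lower limit for the later one; the end of the later date's known period is an upper limit for the earlier one.
- If no feasible date exists, query the site.
- Flag imputed dates in the listings and report how many were adjusted.
- State whether the rule also covers a partial diagnosis date; the present wording is limited to endpoints.

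**Cost.** One corrected formula, one short rule and a small date routine. The adjusted date is still a guess, and the nearest feasible date lies at the edge of the interval. In the response example it gives 1 day, where the interval midpoint (21 February) would give 49. Where no other date narrows the interval for an end date, the rule amounts to the reset-to-day-1 row above, which moves Q1 by less than 2 days at a 6-month median.

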8.7.4 Safety endpoints

PFIZER CONFIDENTIAL

All adverse events collected on the DCT will be listed and summarized for all data reporting milestones. Adverse Events will be coded using the latest Medical Dictionary for Regulatory Activities (MedDRA) version. The version used will be indicated in the data summaries and listings.

All patients who discontinue treatment due to safety reasons such as AEs, will be captured and reported as a reason for discontinuation in the patient disposition summaries and listings.

All Adverse Event data captured will be listed. In addition a separate listing will be presented for Serious Adverse Events.

The number and percentage of patients reporting at least one Adverse Event will be summarized within the following categories:

- Adverse Events
- Treatment-related
- Serious
- Serious treatment-related

The following summary tables will also be presented:

- Number and percentage of patients and number of Adverse Events by MedDRA System Organ Class (SOC) and Preferred Term (PT);
- Serious Adverse Events by SOC and PT.

[figure not shown]
SOC and PT will be presented in decreasing frequency of the total number of patients with Adverse Events. If a patient experienced more than one Adverse Event, the patient will be counted once for each SOC and once for each PT.

